- A) To evaluate the effects of rivaroxaban on plasma markers of coagulation activation, inflammation and markers of endothelial cell activation in SCD patients during the non-crisis, steady state.
- B) To evaluate the effects of rivaroxaban on microvascular blood flow in SCD patients during the non-crisis, steady state.
- C) To evaluate the safety of rivaroxaban in patients with SCD

Hypotheses/Estimates: Our primary hypothesis is that inhibition of factor Xa with rivaroxaban will reduce inflammation, coagulation and endothelial cell activation in patients with SCD.

Title of the Protocol: The effect of factor Xa inhibition, with rivaroxaban, on the pathology of sickle cell disease

Criteria for Evaluation:

Efficacy: Primary Endpoints: *Soluble vascular cell adhesion molecule-1 (VCAM-1) and interleukin-6 (IL-6):* Plasma levels of soluble VCAM-1 and IL-6 will be obtained at Baseline, and then at weeks 2 and 4 during both Treatment Phases. The primary efficacy measure will be a comparison of the difference between the measurements following 4 weeks of treatment with rivaroxaban/placebo and baseline measurements.

Exploratory Endpoints: *Markers of Coagulation Activation, Endothelial Activation, and Inflammation:* We will measure plasma levels of markers of coagulation activation (thrombinantithrombin [TAT] complexes and D-dimer), other markers of endothelial activation (soluble ICAM) and other markers of inflammation (high sensitivity CRP, MPO, IL-2, IL-8, TNFα, sPLA2), at Baseline and then at weeks 2 and 4 during the Treatment Phases.

Microvascular blood flow: We will analyze microvascular blood flow using laser Doppler velocimetry (LDV) assessments of post-occlusive reactive hyperemia (PORH). Measurements will be obtained at baseline and at 4 weeks during the Treatment Phases.

Safety Assessment: We will evaluate patients for treatment-related complications for the duration of the study. Major bleeding complications (any bleeding episode into critical sites, e.g. intracranial bleed, decrease in hemoglobin concentration of at least 2g/dL from baseline or any prolonged bleeding that requires a blood transfusion), and other clinically relevant non-major or trivial bleeding will be recorded. We will also evaluate for episodes of SCD-related events, including acute pain episodes during scheduled follow up visits

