Safety Assessment: We will evaluate patients for major bleeding complications (any bleeding episode into critical sites, e.g. intracranial bleed, decrease in hemoglobin concentration of at least 2g/dL from baseline or any prolonged bleeding that requires a blood transfusion) and other clinically relevant non-major or trivial bleeding. We will also evaluate for episodes of SCD-related events during scheduled follow-up visits, by employing a systems review, physical examination, vital signs, and routine laboratory tests.

Termination Criteria: Treatment with study drug will be discontinued at any time if the patient: a) withdraws consent; b) develops a major bleeding episode (defined as any bleeding episode into critical sites, e.g. intracranial bleed, decrease in hemoglobin concentration of at least 2g/dL from baseline or any prolonged bleeding that requires a blood transfusion); or if, c) in the judgment of the investigator, continuation of the study drug will be hazardous to the patient. The UNC DSMB will review the protocol following the occurrence of the 1st treatment-related serious adverse event. The study will be terminated at the occurrence of treatment-related serious adverse events, including major bleeding, in up to 3 study participants.

STATISTICAL METHODS

Normally distributed variables will be presented with means and SD, while summary of variables not normally distributed will be presented with medians and ranges or geometric means and SD as appropriate. The main study objective is to examine the difference between the measurements at baseline and following 4 weeks of treatment. We will evaluate the effect of rivaroxaban on the outcome measures by performing a comparison of treatment by visit using paired t-tests subsequently followed by crossover ANOVA model testing to assess the carry-over effect and treatment effect. In addition, when outcome measures are not normally distributed, we will perform appropriate nonparametric tests. The effect of rivaroxaban on various plasma markers and microvascular blood flow will be estimated using a multiple linear regression model. While the study is adequately powered to evaluate the effect of rivaroxaban on soluble VCAM-1 and IL-6, analysis of the effect of rivaroxaban on the other indicated endpoints are exploratory.

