Sample Size Justification: The primary outcome measures are sVCAM-1 and IL-6. Based on our preliminary data in SCD patients, log (sVCAM) and log(IL-6) are normally distributed with SD of 0.49 and 0.95, respectively. In a 2x2 crossover design, assuming a correlation of 0.65 for the pre- and post-treatment measures, to detect a difference of 0.245 in the change of log(sVCAM) and 0.475 in the change of log(IL-6) between the rivaroxaban and placebo groups requires a minimum sample size of 15 per sequence (a total sample size of 30) at 80% power and $\alpha = 0.05$. Assuming a 10% dropout rate, a total of 34 patients is required for this study (17 in each sequence).

Data Management: A standardized set of data collection forms will be designed using the RED Cap system and a secure database will be created. All data will be stored under password protection on a secured server. A data manager will handle all data entry and database security. This individual will work closely with the statistician on database design and quality assurance procedures.

Timeline: We anticipate beginning recruitment in year 2, following studies on rivaroxaban in sickle mice. Recruitment for this clinical study is expected to take up to 36 months. The remaining few months will be dedicated to completing the studies, data analysis and publication.

HUMAN SUBJECTS

Protection of Human Subjects

1. Human Subjects Involvement and Characteristics: This study seeks to evaluate the efficacy and safety of the factor Xa inhibitor, rivaroxaban, in SCD. Thirty two patients with SCD (HbSS or S β^0 thalassemia) that meet the eligibility criteria will be enrolled in a randomized, double-blind, placebo-controlled, crossover trial. At the time of enrollment, all study subjects will be in the non-crisis, steady state. Informed consent will be obtained according to IRB approved procedure. Patients will be closely monitored for adverse events following randomization to the study drug. The primary goal of this study is to evaluate the effect of rivaroxaban on plasma levels of soluble VCAM and IL-6. Furthermore, we will evaluate plasma other markers of endothelial activation (soluble ICAM) and other inflammatory markers (high sensitivity CRP, MPO, IL-2, IL-8, TNF α , sPLA2), coagulation activation (TAT and D-dimer),

assessment of microvascular blood flow using laser Doppler velocimetry and safety as described in the application.

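### Analysing sVCAM-1 and IL-6 as change from each period's baseline gives up precision that a baseline-adjusted week-4 crossover model would recover; the size of the gain depends on correlations the plan does not give

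*Combined protocol and SAP*

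**What the plan says.** Under Criteria for Evaluation (Efficacy), the combined protocol and SAP defines the primary measure as change: "The primary efficacy measure will be a comparison of the difference between the measurements following 4 weeks of treatment with rivaroxaban/placebo and baseline measurements". Sampling is described as "Plasma levels of soluble VCAM-1 and IL-6 will be obtained at Baseline, and then at weeks 2 and 4 during both Treatment Phases". The laboratory studies repeated after washout are to serve as the second period's baseline, and the schedule of assessments lists biomarkers at the baseline of both treatment periods.

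Statistical Methods repeats the change framing: "The main study objective is to examine the difference between the measurements at baseline and following 4 weeks of treatment". It proposes "performing a comparison of treatment by visit using paired t-tests subsequently followed by crossover ANOVA model testing to assess the carry-over effect and treatment effect". It adds that "when outcome measures are not normally distributed, we will perform appropriate nonparametric tests", and that the effect on plasma markers and blood flow "will be estimated using a multiple linear regression model". None of these is labelled primary, no model terms are listed, and no consequence is attached to the carry-over test.

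Sample Size Justification also works in change. The SDs on the log scale are 0.49 and 0.95, the differences to detect are 0.245 and 0.475, the pre/post correlation is 0.65, and 30 patients are said to give 80% power at α = 0.05. The total with 10% dropout is 34.

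**The concern.** Subtracting the baseline is the same as adjusting for it with a slope fixed at 1. In a crossover each patient already serves as his or her own control, so the period baseline is needed only to remove within-patient drift between the periods. If the week-4 difference between periods tracks the baseline difference with a slope well below 1, subtracting the whole baseline difference adds noise.

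At stake is the precision of the two primary comparisons in a trial of about 30 completers. The baselines are collected in any case. The question is only whether the analysis uses them well.

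**Working it through.** **Inputs from the plan.** Effect 0.5 SD for both markers (0.245/0.49 and 0.475/0.95); pre/post correlation r = 0.65; 30 completers.

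**Assumptions.** Two-sided 0.05 for each endpoint (the plan states neither sidedness nor a split over two endpoints); equal variance at all four visits; no carry-over; and the between-period correlations, which the documents do not give. Write *a* for the correlation between periods at the same visit (baseline with baseline, week 4 with week 4) and *c* for the correlation between periods across visits (baseline with week 4).

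**The plan's own figure.** With a within-patient contrast variance of 2(1 − 0.65) = 0.70 SD², a t-based calculation gives N = 26 at two-sided 0.05 (88.5% power at N = 30). It gives exactly N = 30 (81.1% power) if α is split to 0.025 per endpoint, which the plan does not say. 30/0.9 = 33.3, which rounds up to an even 34. For 30 patients to give 80% power at two-sided 0.05, the contrast variance must be 0.890 SD².

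**Formulas**, per patient, for the difference between periods, in SD² units:

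- Week-4 difference and baseline difference: variance 2(1 − a) each, covariance 2(r − c).
- Best slope: b = (r − c)/(1 − a).
- Change score: 4(1 − a)(1 − b).
- Baseline-adjusted week-4 value: 2(1 − a)(1 − b²).
- Ratio, adjusted to change: (1 + b)/2. Estimating the slope multiplies this by 1 + 1/(30 − 4) = 27/26.

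The adjusted model therefore wins whenever b < 25/27 ≈ 0.93. Its worst case, b = 1, costs 27/26 − 1 ≈ 4% of variance.

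**Structure A: all cross-period correlations equal (a = c = q).** The change variance is 4(1 − 0.65) = 1.40 at every q, with power 60.8%.

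| q | best slope | adjusted variance (× 27/26) | reduction | power, adjusted | power, week 4 without baseline |
|---|---|---|---|---|---|
| 0 | 0.65 | 1.155 (1.199) | 14.3% | 67.4% | 46.4% |
| 0.3 | 0.50 | 1.050 (1.090) | 22.1% | 71.5% | 60.8% |
| 0.5 | 0.30 | 0.910 (0.945) | 32.5% | 77.5% | 75.3% |
| 0.65 | 0 | 0.700 (0.727) | 48.1% | 87.2% | 88.5% |

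On the ratio scale, the 95% CI factor for sVCAM-1 goes from ×/÷ 1.24 to between 1.22 and 1.17, and for IL-6 from ×/÷ 1.52 to between 1.48 and 1.35.

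**Structure B: change has the stated 80% power.** Setting 4(1 − a)(1 − b) = 0.890 fixes *c* for each *a*.

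| a | c | best slope | adjusted variance (× 27/26) | reduction | power, adjusted |
|---|---|---|---|---|---|
| 0 | −0.13 | 0.78 | 0.791 (0.822) | 8% | 83% |
| 0.3 | 0.17 | 0.68 | 0.749 (0.778) | 13% | 85% |
| 0.5 | 0.37 | 0.55 | 0.692 (0.719) | 19% | 88% |
| 0.65 | 0.52 | 0.36 | 0.607 (0.631) | 29% | 91% |

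**Structure C: change contrast variance 0.70.** The same steps give best slopes of 0.825, 0.75, 0.65 and 0.50, and reductions of about 5%, 9%, 14% and 22%.

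**Decaying correlation.** With 0.65^(weeks/4) at weeks 0, 4, 6 and 10, the variances are 1.598 (change) and 0.927 × 27/26 = 0.963 (adjusted): about 40% lower, with power 55% against 77%.

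**Where the gain comes from.** At low between-period correlation it comes from the covariate. At high correlation it comes mainly from no longer fixing the slope at 1. In structure A at q = 0.65 the covariate costs about one point of power against week-4 values alone. In structure B at a = 0.65, week-4 values alone have variance 0.70, already 21% below 0.890, and the covariate takes this to 0.631.

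**The case against.** **The gain rests on correlations that are not in the documents.** This stands. A reader might infer from structure A that the cut is at least 14% and may reach 48%. The documents do not support that. Structure A takes all cross-period correlations as equal, and the change score then has 60.8% power rather than the stated 80%. Where change does have 80%, the cut is about 8% to 29%, so 14% is not a floor. For the same reason 60.8% is not the power implied by the plan's inputs alone.

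**The change score is a valid endpoint, and the sizing is framed on it.** Also true. The trial is described as proof-of-concept, and no bias is alleged. Any carry-over into the second baseline would affect the change score and the covariate alike, so neither has an advantage there.

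**The planned multiple linear regression may already include baseline.** It may, but its covariates are not listed and it is not designated primary.

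**The open choice of method does little harm.** A reader might infer that the unranked tests or the carry-over test inflate type I error. The documents do not show this. In simulation, reporting the smaller p of the paired t-test and the crossover ANOVA kept the error at about 5%. Inflation through carry-over would need a rule that switches the analysis after a positive test, and the plan states no such rule. By themselves, the missing primary label and carry-over rule are gaps in detail.

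**Conclusion.** The concern holds as a matter of precision. sVCAM-1 and IL-6 are judged on change with no baseline adjustment stated. A week-4 crossover model with the period baseline as covariate was more precise in every structure examined, from data already scheduled. The variance reduction with 30 completers is illustrative: 14% to 48% under equal cross-period correlations, about 8% to 29% if change has its stated 80% power, and about 5% to 22% if the change contrast has variance 0.70 SD². The direction needs only a best slope below about 0.93, and the downside is capped at about 4% of variance. The figures assume equal variances, no carry-over and two-sided 0.05 per endpoint. This is a worthwhile, inexpensive improvement; the planned analysis is not invalid.

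**What to change.** Name one primary analysis. For log(sVCAM-1) and log(IL-6) at week 4, fit a linear mixed model with fixed effects for treatment, period and sequence and a random patient effect. Enter the period baseline as two terms: the within-patient deviation and the patient mean. The split matters. In simulation with equal cross-period correlations of 0.65, a single common slope cut the variance by only about 31%, against about 47% for the within-patient model. Report the rivaroxaban-to-placebo ratio with its 95% CI.

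Report carry-over descriptively, and state that it does not change the primary analysis. Keep the change-score and nonparametric analyses as sensitivity analyses.

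The cost is SAP wording and one degree of freedom (27 instead of 28 with 30 completers). No new samples, visits or patients are needed.

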Overview: As a result of the presence of macrovascular thrombotic complications, as well as the biochemical evidence of ongoing coagulation activation, sickle cell disease (SCD) is often referred to as a "hypercoagulable state." SCD is characterized by increased tissue factor expression, increased levels of plasma markers of thrombin generation and fibrinolysis, increased platelet activation and decreased levels of natural anticoagulant proteins. Despite the abundant laboratory evidence of hypercoagulability observed in these patients, it still remains uncertain whether the observed coagulation activation contributes to the vascular occlusive episodes that characterize SCD. However, recent studies suggest that certain SCD-related complications, including thrombotic stroke, may be associated with coagulation activation. In addition, inhibition of tissue factor abrogated the activation of coagulation and attenuated inflammation and endothelial cell injury as demonstrated by reduced plasma levels of IL-6, serum amyloid P. soluble vascular cell adhesion molecule-1 and decreased levels of myeloperoxidase in the lungs of sickle cell mice, suggesting a cross-talk between coagulation and inflammation in SCD. The treatment options for SCD remain limited. Although the low molecular weight heparin, tinzaparin, has been reported to significantly reduce the duration of acute pain episodes, it remains uncertain whether this effect is due to its anticoagulant or anti-adhesive actions. In this study, we will evaluate the efficacy and safety of rivaroxaban in SCD. If the data support the hypothesis that rivaroxaban is effective and safe in this setting, we plan on carrying out adequately powered studies to more definitively evaluate its safety and efficacy in the treatment and/or prevention of selected SCD-related complications.

Intervention: We will conduct a randomized, double-blind, placebo-controlled, crossover trial of rivaroxaban (n = 34). After baseline assessments are performed, subjects will receive rivaroxaban 20 mg/day or placebo for 4 weeks, separated by a 2 week washout phase. At the end of the washout period, a repeat history and examination and laboratory studies will be performed which will serve as a baseline for the second treatment phase, and patients will receive either rivaroxaban or placebo, depending on their first treatment administration.

IND Holder: [name]

Specific Aims:

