Study Design: This is a randomized, double-blind, placebo-controlled, crossover study of rivaroxaban to evaluate the efficacy and safety of rivaroxaban in SCD. It will be divided into a Screening/Baseline phase, Treatment phase, and Follow-up phase.

Study Population: Thirty two patients with SCD (HbSS or HbS β^0 thalassemia) between the ages of 18 and 65 who meet the eligibility criteria and provide consent to participate in the study, will be randomized in this crossover trial.

Clinical and Laboratory Evaluations: The Screening/Baseline Phase will occur within 28 days of study drug administration and will include: informed consent, a history and physical examination, and clinical laboratory tests including: a complete blood count, routine coagulation studies, routine chemistries to assess liver and renal function chest x-ray, brain MRI/MRA scan and serum or urine pregnancy test (if female, and of child-bearing capacity). During the Treatment Phase, we will also obtain a complete blood count, routine chemistries to assess liver and renal function, and pregnancy test (if female); and prior to the second treatment phase, a repeat history and examination and laboratory studies will be performed, which will serve as a baseline for the second treatment phase. Finally, measurements of microvascular blood flow (assessed non-invasively using laser Doppler velocimetry), endothelial activation (soluble VCAM, soluble ICAM), coagulation activation (TAT and D-dimer) and markers of inflammation (IL-6, high sensitivity CRP, MPO, IL-2, IL-8, TNF α , sPLA2) will be obtained at specified time points during the Baseline, Treatment and Washout/Follow-up Phases. The Follow-up Phase will consist of safety assessments performed four weeks after the final dose of study treatment.

Title of the Protocol: The effect of factor Xa inhibition, with rivaroxaban, on the pathology of sickle cell disease

Sample Size: In a 2x2 crossover design, assuming a correlation of 0.65 for the pre- and posttreatment measures, to detect a difference of 0.245 in the change of log(sVCAM) and 0.475 in the change of log(IL-6) between the rivaroxaban and placebo groups requires a minimum sample size of 15 per sequence (a total sample size of 30) at 80% power and α =0.05. Assuming a 10% dropout rate, a total of 34 patients is required for this study (17 in each sequence).

Randomization: 1:1 randomization to receive rivaroxaban or placebo.

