We will conduct a randomized, double-blind, placebo-controlled, crossover study to evaluate the efficacy and safety of rivaroxaban in SCD. We have selected this agent based on our preliminary data in sickle mice showing that 'upstream' TF inhibition achieves the desired effects on inflammation and endothelial activation, but that 'downstream' thrombin inhibition does not. The study will consist of three phases: 1) Screening/Baseline; 2) Treatment; and 3) Follow-up. The Screening/Baseline Phase will occur within 28 days of study drug administration and will include: informed consent, a history and physical examination, and clinical laboratory tests including: a complete blood count, routine coagulation studies, routine chemistries, chest x-ray, and serum or urine pregnancy test (if female, and of child-bearing capacity). The sequence of drug administration will be generated via block permuted randomization procedure. The 4-week Treatment Phase will consist of drug administration, efficacy assessments and safety assessments (including pregnancy testing in females of child-bearing capacity). After the first treatment period, there will be a washout period of 14 ± 3 days. In the second treatment phase, patients will be crossed over to receive rivaroxaban or placebo, depending on their initial treatment assignment. The total duration of the Treatment phase (including washout) will be 10 weeks. During the Follow-up Phase at week 12, patients will obtain their final study evaluation. Table 2 provides a detailed schedule of assessments for the study period.

Treatment: Subjects will receive rivaroxaban 20 mg/day (the approved dose to prevent stroke and systemic embolism in patients with non-valvular atrial fibrilation) and placebo for 4 weeks each, separated by a 2-week washout phase. Pill counting will be used to assess compliance. PT/INR will be monitored by an unblinded investigator to assess compliance with no other involvement in the study). If major bleeding or other serious adverse event occurs (see Appendix 2), the study drug will be discontinued and the patient followed until resolution of the problem. Subjects that discontinue the study early will not be replaced.

Eligibility Criteria:

Inclusion Criteria:

- a) 18 to 65 years of age;
- b) HbSS or HbS β 0 thalassemia; serum creatinine $\leq 1.0 \text{ mg/dL}$ men) or 1.2 mg/dl (women);
- c) ALT ≤ 2 times upper limits of normal;
- d) platelet count \geq 150,000 cu/mm;

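### The stated 80% power with 30 completers does not follow from the plan's SDs and pre/post correlation (about 61% if a patient's two changes are uncorrelated), and enrolment is given as both 34 and 32

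*Combined protocol and SAP*

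**What the plan says.** Statistical Methods, Sample Size Justification gives SDs of 0.49 for log(sVCAM) and 0.95 for log(IL-6). It then proceeds "assuming a correlation of 0.65 for the pre- and post-treatment measures, to detect a difference of 0.245 in the change of log(sVCAM"; the corresponding target for IL-6 on the log scale is 0.475. Both targets compare rivaroxaban with placebo. That section and the Sample Size paragraph of the synopsis both conclude that this "requires a minimum sample size of 15 per sequence (a total sample size of 30) at 80% power" with alpha 0.05. Ten per cent dropout raises the total to 34.

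The primary variable is a change from baseline. Under Criteria for Evaluation, Efficacy: "The primary efficacy measure will be a comparison of the difference between the measurements following 4 weeks of treatment with rivaroxaban/placebo and baseline measurements". The laboratory work repeated after washout is one "which will serve as a baseline for the second treatment phase", so each period has its own baseline.

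Statistical Methods then asserts: "While the study is adequately powered to evaluate the effect of rivaroxaban on soluble VCAM-1 and IL-6".

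On enrolment, the Overview describes a "crossover trial of rivaroxaban (n = 34"), in agreement with both sample-size paragraphs. Study Population in the synopsis and Human Subjects, item 1 each say "Thirty two patients with SCD" instead. Under Treatment: "Subjects that discontinue the study early will not be replaced".

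**The concern.** The SDs given are those of the log levels. The single correlation links a pre-treatment to a post-treatment value, which fixes the variance of one change. The treatment comparison in this crossover is a difference between two such changes in the same patient, so its variance also needs the correlation between those changes. The plan does not give that correlation, the SD of the contrast, the sidedness of the test, or any division of alpha between the two primary markers.

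If the study has nearer 61% than 80% power at the planned difference, a null result on either marker would be weak evidence of no effect. A reader relying on the statement in Statistical Methods would over-read it, and the Overview says these data will decide whether larger studies follow.

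The two enrolment totals matter because one of them, under the plan's own dropout rate, misses the plan's own minimum number of completers.

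**Working it through.** **Inputs from the documents.** SD of log level: 0.49 (sVCAM) and 0.95 (IL-6). Pre/post correlation: 0.65. Differences in change: 0.245 and 0.475. Completers: 30. Power 80%, alpha 0.05. Dropout: 10%.

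**Standardised effect.** 0.245/0.49 = 0.5 and 0.475/0.95 = 0.5. Both markers have the same target in SD units, so one calculation serves both.

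**Variance of the contrast, in units of SD².**
- One change: 2(1 − 0.65) = 0.70.
- Difference between a patient's two changes: 2 × 0.70 × (1 − c) = 1.40(1 − c), where c is the correlation between the two changes.
- If all four measurements share the correlation 0.65, the two changes have covariance 0.65 − 0.65 − 0.65 + 0.65 = 0. So c = 0 and the variance is 1.40.

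**Power.** Noncentral t, df = N − 2 = 28, noncentrality 0.5 × √30 / √variance.

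The stated 80% first: at two-sided 0.05 it requires a variance of at most 0.890, so c = 1 − 0.890/1.40 = 0.364. The contrast SD would have to be at most √0.890 × 0.49 = 0.462 for log(sVCAM) and √0.890 × 0.95 = 0.896 for log(IL-6). With c = 0 these SDs are √1.40 × 0.49 = 0.580 and √1.40 × 0.95 = 1.124.

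The values of c below are assumptions, since the documents give none.

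| Assumption | Variance (SD²) | Power, N = 30, two-sided 0.05 |
|---|---|---|
| c = −0.25 | 1.75 | 52% |
| Correlation decaying as 0.65^(weeks/4), measurements at weeks 0, 4, 6, 10 | 1.60 | 55% |
| c = 0 | 1.40 | 61% |
| c = 0.25 | 1.05 | 73% |
| c = 0.364 | 0.890 | 80% |
| c = 0.5 | 0.70 | 88% |

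With c = 0:
- One-sided 0.05 gives 73%.
- Completers needed for 80%: 46 two-sided, or 38 one-sided with equal sequences.
- Difference detectable with 80% power at N = 30, two-sided: 0.627 SD, which is 0.627 × 0.49 = 0.307 and 0.627 × 0.95 = 0.596. These are about 25% above the planned 0.245 and 0.475 (0.627/0.5 = 1.25).

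**Other calculations that land on or near 30.**
- A single paired difference (variance 0.70) at two-sided 0.025: 81.1% at N = 30. At two-sided 0.05 the same variance gives 88.5%, and 26 would be enough.
- A baseline-adjusted contrast, variance 2(1 − 0.65²) = 1.155, at one-sided 0.05: 79.98%. At two-sided 0.05 it gives 69%.

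The sample-size text states neither.

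**Enrolment.** 30/0.9 = 33.3, rounded up to 34, which reproduces the stated total. Expected completers are 34 × 0.9 = 30.6, against 32 × 0.9 = 28.8. With c = 0, power at 28 to 29 completers is 58% to 59%.

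**The case against.** The strongest reply is that this is a reporting gap and not a demonstrated shortfall. Plausible values of c lie on both sides of the one that gives 80%, and nothing in the plan says that the two changes are uncorrelated. Thirty is also the exact minimum for a single paired difference at two-sided 0.025 (79.5% at 29, 81.1% at 30), and 0.025 is what an even split of 0.05 over two primary markers would give. Statistical Methods names paired t-tests of treatment by visit first. If that means week 4 on rivaroxaban against week 4 on placebo, and 0.65 also holds across periods, the variance is 0.70 and power is 88% at 30 completers and 86% at 28. On this view the study is a proof of concept, and it is enough to ask for the missing inputs.

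Much of this stands. The calculation does not show that 30 is too few, and the sponsor may have used coherent inputs and left one out. But each of these readings departs from the text. The first changes the stated alpha and drops the two-change contrast. The second replaces the difference in change named in both the efficacy criteria and the sample-size justification. The plan's unqualified statement about power therefore has no stated basis.

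The enrolment conflict needs no assumption. Its effect on power is small, and it is a separate correction.

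**Conclusion.** The concern holds. On the plan's own change-score contrast, 80% power at 30 completers cannot be derived from the stated SDs and the pre/post correlation. Power is about 61% at two-sided 0.05 if a patient's two changes are uncorrelated. It ranges from 52% to 88% as c goes from −0.25 to 0.5, a range chosen for illustration. A value of c near 0.36, or a different test or alpha, would restore 80%, but none is stated. Confidence is high that the figure is not derivable as written; whether the study is in fact underpowered depends on the missing correlation.

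The totals of 34 and 32 contradict each other in current text. Only 34 follows from 30 completers and 10% dropout.

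**What to change.** 1. **If the sponsor holds data that support 80%:** in both sample-size paragraphs, state the SD of the within-patient contrast, the between-period correlation of the changes, and their source.
2. **If not:** replace the power statement with wording such as: *With 30 completers and two-sided alpha 0.05, power for the difference between the two period changes is about 61% if a patient's two changes are uncorrelated (52% to 88% for assumed correlations of −0.25 to 0.5). In the uncorrelated case, 80% power is reached for differences of 0.307 in log(sVCAM) and 0.596 in log(IL-6).*
3. **Either way:** state whether alpha is one- or two-sided and whether it is divided between the two markers. If it is divided, recompute the power figures at the divided level.
4. Qualify the claim of adequate power in Statistical Methods to match.
5. Change 32 to 34 in Study Population and in Human Subjects, item 1.

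The cost is protocol wording only. It needs no extra patients and no change to the primary variable. The stated power becomes less favourable unless the missing correlation is documented.
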